6.4 Concomitant Therapy

Any medication or vaccine included over-the-counter or prescription medicines, vitamins, and/or herbal supplements that the participant is receiving at the time of enrolment or receives during the study must be recorded along with:

- Reason for use
- Dates of administration including start and end dates
- Dosage information including dose and frequency

List of the restricted and prohibited medications can be found in [Table 5](#) and [Table 6](#), provided below:

Table 5 **Restricted Medications**

Medication/class of drug:	Recommendation (including limits for duration permitted and special situations in which it is allowed):
Inactive/killed vaccinations (eg, inactive influenza)	Not allowed within the 5 days before or within 5 days after any IP dosing study visit.
COVID-19 vaccinations (eg, whole virus, protein subunit, nucleic acid, viral vector)	If COVID-19 vaccination is in the best interest of the participant and the participant is vaccinated during the study, IP dosing can continue but the recommendation is that IP dosing should not occur within 14 days before and 28 days after a dose of vaccine. As these intervals might change, please discuss with the study physician for the most current recommended time interval, prior to any vaccine dose. Refer to section 6.4.2 for more details.
Any Immunosuppressive – topical	Topical administration of Immunosuppressive medication may be allowed at the discretion of the Investigator.
Allergen Immunotherapy	Allowed if on stable therapy started 30 days prior to V1; no change during the treatment period. Should not be administered on the same day as study intervention administration.
Decongestants (topical or systemic)	Only allowed for endoscopic procedure.

Medication/class of drug:	Recommendation (including limits for duration permitted and special situations in which it is allowed):
Systemic Corticosteroids as maintenance treatment	Not allowed 3 months prior to V1. During study conduct, SCS are allowed as a rescue to relieve NP worsening of symptoms, to treat asthma exacerbations or to treat other indications at PI's discretion. However, it is recommended that participants abstain from using SCS for the first 3 months after randomisation, unless in case of an emergency or if it is deemed necessary by the PI.

Table 6 Prohibited Medications

Prohibited medication/class of drug:	
Corticosteroid-eluting intranasal stents	Not allowed 6 months prior to V1 or during the study.
Intranasal Medication including intranasal corticosteroids drops	Only study provided MFNS or equivalent INCS is allowed.
Any immunosuppressive treatment including but not limited to: methotrexate, cyclosporine, mycophenolate, tacrolimus, gold, penicillamine, sulfasalazine, hydroxychloroquine, azathioprine, cyclophosphamide	Not allowed within 3 months prior to V1; during the study period and 3 months or 5 half-lives (whichever is longer) after last dose of the IP.
Aspirin desensitisation	Use of aspirin as a desensitisation regimen for the management of aspirin exacerbated respiratory disease (AERD) is not allowed; all other uses of aspirin are allowed for any other medical conditions.
Any marketed or investigational biologic (monoclonal or polyclonal antibody)	Not allowed within 4 months or 5 half-lives (whichever is longer) prior to V1; during screening/run-in and throughout the IP treatment, and 4 months or 5 half-lives (whichever is longer) after the last dose of IP.
Other investigational product	Not allowed within 30 days or 5 half-lives (whichever is longer) prior V1, during screening/run-in and throughout the IP treatment and preferably 4 weeks after the last dose of IP.
Live attenuated vaccines	Not allowed within 30 days prior to randomisation; during the study period, and 16 weeks or 5 half-lives (whichever is longer) after the last dose of the IP.
Blood products or immunoglobulin therapy	Not allowed 30 days prior to Visit 1, during screening/run-in and throughout the IP treatment and preferably 4 weeks after the last dose of IP.
Herbal remedies for the treatment of CRSwNP	Not allowed 30 days prior to Visit 1, during screening/run-in and throughout the IP treatment and preferably 4 weeks after the last dose of IP.

The Medical Monitor should be contacted if there are any questions regarding concomitant or

prior therapy.

Participants must abstain from taking prescription or non-prescription drugs for nasal polyps (including vitamins and dietary or herbal supplements) within 7 days (or 14 days if the drug is a potential enzyme inducer) or 5 half-lives (whichever is longer) before the start of study intervention until completion of the follow-up visit, unless, in the opinion of the investigator and sponsor, the medication will not interfere with the study.

6.4.1 Background Medication

The aim of this study is to evaluate the treatment effect of tezepelumab on polyp reduction. Therefore, the background INCS medications should be maintained at a stable dose from Visit 1 and throughout the screening and study period and no other medications intended to prevent polyp recurrence should be used. All participants will use INCS for a minimum of 4 weeks prior to V3 and continued throughout the study period.

Standardised MFNS (50 µg/actuation) nasal spray is contained in a bottle that contains 120 actuations for US and 140 actuations for all other countries. Two doses of MFNS (50µg/actuation) in each nostril twice daily (total 400µg daily) or equivalent INCS will be administered unless there is a medical rationale to use the lower dose (QD) regimen.

Equivalent dose should refer to the highest approved country INCS dose for CRSwNP. The generic name of the INCS and the total daily dose should be recorded in the eCRF.

6.4.2 COVID-19 Vaccination

As there is an expected broad vaccination against COVID-19 virus in most countries, the CSP allows participants to be vaccinated following certain precautions.

[figure not shown]
COVID-19 vaccines are either nucleic acid vaccines (which can include DNA plasmid and mRNA), recombinant vector vaccines (non-replicating viral vectors) or inactivated virus vaccines. DNA plasmid and mRNA vaccines are considered an inactivated vaccine. Recombinant vector candidates potentially may be in a new category. Based on available publications on mRNA and virus vector anti-SARS-CoV-2 vaccines, the immune response developed rapidly after both the prime vaccine and the booster dose. No live attenuated COVID-19 vaccines are currently available. For vaccines that are currently approved under emergency use authorisation (EUA), please refer to the relevant health authority websites for further guidance. As per this CSP, any live attenuated vaccine is prohibited during study conduct.

Given the limited long-term safety data of COVID-19 vaccines and the potential to confound the interpretation of safety results in the study, the following COVID-19 vaccination guidance should be followed depending on the study phase of the participant. As the below intervals

might change, please consult with the study physician for the most current recommended time interval prior to any vaccine dose.

Study Period	Recommendations
Participant in screening/run-in period	
If COVID-19 vaccination is in the best interest of the participant and they are vaccinated or scheduled to be vaccinated before the screening or run-in visit, the randomisation visit should be scheduled to ensure that the first IP dose is administered at least 28 days after any vaccination dose.
Participant in treatment period	
If COVID-19 vaccination is in the best interest of the participant and they are vaccinated during the study, IP dosing can continue but IP is not recommended to be administered within 14 days before or 28 days after a dose of vaccine.If the participant receives a COVID-19 vaccination less than 14 days from the last IP dose, the next IP administration is recommended to be rescheduled or skipped to ensure the next IP dose is at least 28 days after the vaccine administration.The participant's COVID-19 vaccination schedule should follow country-specific health authority guidelines. Vaccination against COVID-19 should be planned in advance to ensure the IP dosing/COVID-19 vaccination intervals are maintained.Study visits should still be conducted within the protocol-specified time window, even if a participant receives a COVID-19 vaccine dose. However, even if IP is not administered at a study visit because of COVID-19 vaccination restrictions, other site visit assessments should still be performed according to the CSP schedule.At every study visit during the treatment period, the investigator must ask if the participant has received or is planning to receive a COVID-19 vaccination. This is to ensure that the required time interval for IP dosing (mentioned above) is maintained.If it is anticipated that a participant will miss 2 consecutive IP administrations, the AstraZeneca study physician should be contacted to discuss further patient participation in the study.The reason for skipping IP administration should be recorded with “COVID-19” prefix in medical records, protocol deviation and COVID-19 related eCRF modules.
Patient in Follow-up period	
If COVID-19 vaccination is in the best interest of the participant, COVID-19 vaccination could be administered. The participant should follow the schedule of assessments listed in CSP in the Schedule of Assessments (SoA, Section 1.3); no special adjustments are needed.It is advised that the participant wait for 14 days after the last IP dose.

Figure 3 COVID-19 Vaccination Administration in Relation to IP Dosing

Reporting of COVID vaccination:

- COVID-19 vaccine details including vaccine's name/manufacturer, route of administration, and vaccination date should be entered without delay into the eCRF CM module. This includes any history of COVID-19 vaccination.
- If a participant experiences an AE/SAE associated with COVID-19 vaccination, the investigator should record this in source document and determine whether the IP should be continued, skipped, or permanently discontinued in accordance with the CSP.

6.5 Study Intervention Compliance

When participants are dosed at the site, they will receive study intervention directly from the investigator or designee, under medical supervision. The date, and time if applicable, of dose administered in the clinic will be recorded in the source documents and recorded in the eCRF. The dose of study intervention and study participant identification will be confirmed at the time of dosing by a member of the study site staff other than the person administering the study intervention.

The study treatment provided for this study will be used only as directed in this Clinical Study Protocol (CSP). The investigational product will be administered at the study site or home (if applicable) on treatment visits and within visit windows as specified in the SoA.

In cases where a treatment visit needs to be rescheduled, the IP must be administered within the visit window or as soon as possible. The PI should make every effort to assure that no IP administrations are missed during the course of the study.

Any change from the dosing schedule, dose interruptions, dose discontinuations should be recorded in the eCRF.

Principal Investigators should also assure that participants are compliant and on a stable dose of the background medication (INCS) during study period.

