IgE FEIA			X																				Section 8.6.1		
Blood for serum and plasma biomarkers			X				X		X		X		X		X		X		X				Section 8.6.1		
Blood for RNA transcriptomic profiling			X				X		X		X		X		X		X		X				Section 8.6.1		
Nasal epithelial lining fluid for PK and Exploratory biomarkers		X ^o	X				X		X								X ⁿ		X				Section 8.6.1		
Staph A Nasal Culture			X						X								X						Section 8.6.1		

Table 1 Schedule of Activities - Screening, Randomisation, Treatment Period, and Follow-Up

Assessment / Activity	Screening	Run-in	Randomisation	Treatment Period																EOT/ IPD	FU all ^d		Additional FU 1 st 200 participants ^c		UNS ^e	Details in CSP section or Appendix
Visit	V1	V2	V3	V4 📞 ^b	V5	V6	V7	V8	V9	V10	V11	V12	V13	V14	V15	V16	V17	V18 📞 ^b	V19	V20 📞 ^b	V21					
Week	-5	-2	0	2	4	8	12	16	20	24	28	32	36	40	44	48	52	58	64	70	76					
Visit window (days) ^a	N/A	±5	±5	±5	±5	±5	±5	±5	±5	±5	±5	±5	±5	±5	±5	±5	±5	±7	±7	±7	±7	N/A	N/A			
Staph A enterotoxin Specific IgE status (only participants in the sub-study) ^o				X																			Section 8.6.1			
Nasal biopsy - tissue for histology and RNA transcriptomics (only participants in the sub-study) ^o				X ^p																			Section 8.6.1			
Genomics Initiative optional, exploratory genetic sample ^q				X																			Section 8.7; Appendix D			
Randomisation, Investigational Product Administration and INCS Management																										
Randomisation				X																			Section 4.1			

Table 1 Schedule of Activities - Screening, Randomisation, Treatment Period, and Follow-Up

Assessment / Activity	Screening	Run-in	Randomisation	Treatment Period															EOT/ IPD	FU all ^d		Additional FU 1 st 200 participants ^c		UNS ^e	Details in CSP section or Appendix
Visit	V1	V2	V3	V4 b	V5	V6	V7	V8	V9	V10	V11	V12	V13	V14	V15	V16	V17	V18 b	V19	V20 b	V21				
Week	-5	-2	0	2	4	8	12	16	20	24	28	32	36	40	44	48	52	58	64	70	76				
Visit window (days) ^a	N/A	±5	±5	±5	±5	±5	±5	±5	±5	±5	±5	±5	±5	±5	±5	±5	±5	±7	±7	±7	±7	N/A	N/A		
IP Administration ^r			X		X	X	X	X	X	X	X	X	X	X	X	X							Section 6.1		
Home IP Administration by HCP (optional) ^s									X	X		X	X		X	X	X							Section 6.2.3	
INCS Distribution ^v	X	X	X		X	X	X	X	X	X	X	X	X	X	X	X	X		X			X	Section 6.4.1		

^a All visits to be scheduled from the date of randomisation, not from the date of previous visit.

^b Visits 4, 18 and 20 is a phone/remote visit (').

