Further details on IP administration are provided in the IP handling instructions. Investigational product administration must be carried out in line with the instructions provided.

At Visits 3 and 5 (Weeks 0 and 4), participants should be observed by the HCP for a minimum of 2 hours after IP administration for the appearance of any acute drug reactions. For the remaining visits involving IP administration, participants will be observed by the HCP (or adult if injection was done at home) for a minimum of 1 hour after IP administration for the appearance of any such reaction.

If any of the following occur, the Investigator should reschedule the visit and the IP should not be administered until the rescheduled visit:

- The participant received allergen immunotherapy injection on the same day as scheduled IP administration.
- The participant has an intercurrent illness that, in the opinion of the Investigator, may compromise the safety of the participant in the study (eg, viral illnesses).
- The participant is febrile ($\geq 38^{\circ}\text{C}$; $\geq 100.4^{\circ}\text{F}$) within 72 hours prior to IP administration.
- The participant is confirmed to have an active COVID-19 infection based on positive SARS-CoV-2 test results.
- The participant is suspected to have an active COVID-19 infection based on assessment of COVID-19 symptoms.
- The participant is planning to receive COVID-19 vaccination during the screening or treatment period. Please refer to section 6.4.2.

The visit should be rescheduled within the allowed visit window and IP should be

administered at that visit. If this is not possible the IP administration should be skipped.

If the participant is suspected to have an active COVID-19 infection or fever ($\geq 38^{\circ}\text{C}$; $\geq 100.4^{\circ}\text{F}$) suspected due to COVID-19 infection, the visit should be rescheduled (and IP administration deferred) and participant should be re-assessed for symptoms of COVID-19 prior to rescheduled visit.

The AstraZeneca study physician should be contacted to discuss further participation in the following situations:

- The participant has been diagnosed with an active COVID-19 infection.
- The participant skips 2 consecutive IP administrations.

If the participant reports an injection site reaction, the Investigator or qualified designee will complete the AE eCRF page and an additional eCRF questions about the injection site reaction.

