- If SCS is used for treatment of NP for ≥ 3 consecutive days, a CT scan and a nasal endoscopy assessment of NPS should be performed prior to first course of treatment with SCS (unless the subject has already had a CT scan prior to a NP surgery post randomisation). If no such assessment is available, an unscheduled visit should be scheduled to obtain those assessments.
- If SCS use for treatment of any other reason than NP is close to V10 (Week 24) or V17 (Week 52), the visit should be rescheduled at least 2 weeks after the last dose of SCS.
- If SCS will be used for any other reason than NP, the investigator is recommended to consult with the AstraZeneca study physician.

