8.4 Overdose

For this study, any dose of study intervention greater than 280 mg administered within a 2-week period will be considered an overdose.

There is currently no specific antidote in the event of overdose of IP. No specific antidote to tezepelumab is available, so adverse reactions should be treated symptomatically as per local standards.

- An overdose with associated AEs is recorded as the AE diagnosis/symptoms on the relevant AE modules in the eCRF and on the Overdose eCRF module.
- An overdose without associated symptoms is only reported on the Overdose eCRF module.

If an overdose on an AstraZeneca study intervention occurs in the course of the study, the investigator or other site personnel inform appropriate AstraZeneca representatives immediately, but **no later than 24 hours** of when he or she becomes aware of it.

The designated AstraZeneca representative works with the Investigator to ensure that all relevant information is provided to the AstraZeneca Participant Safety data entry site.

For overdoses associated with a SAE, the standard reporting timelines apply, see Section [8.3.1](#). For other overdoses, reporting must occur within 30 days.

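### For listed reasons Section 6.2.3 skips a dose that cannot be given in its window, but Section 6.5 lets a rescheduled dose be given late without limit, and a late enough dose meets the protocol's own overdose definition

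*Protocol*

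**What the plan says.** Five parts of the protocol bear on a dose that cannot be given on time.

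- **Section 6.2.3 (Dose Administration)** lists reasons to reschedule a visit: same-day allergen immunotherapy, intercurrent illness judged a safety concern, fever, confirmed or suspected COVID-19, and planned COVID-19 vaccination. The new visit has to fall in the allowed window, and then: "If this is not possible the IP administration should be skipped".
- **Section 6.5 (Study Intervention Compliance)** first says that product is given "on treatment visits and within visit windows as specified in the SoA". It then says: "In cases where a treatment visit needs to be rescheduled, the IP must be administered within the visit window or as soon as possible". The next sentence adds: "The PI should make every effort to assure that no IP administrations are missed during the course of the study".
- **Section 6.4.2 (COVID-19 Vaccination)** deals with a vaccine given less than 14 days after a dose, and advises: "the next IP administration is recommended to be rescheduled or skipped to ensure the next IP dose is at least 28 days after the vaccine". It also keeps study visits inside their windows, with the other assessments done even when product is withheld.
- **Section 8.1.4** covers systemic corticosteroids used for a reason other than nasal polyps close to V10 (Week 24) or V17 (Week 52), and says: "the visit should be rescheduled at least 2 weeks after the last dose of SCS". Week 24 is a dosing visit, and footnote r of the Schedule of Activities makes dosing the last activity of a visit. Section 8.1.4 does not mention dosing.
- **Section 1.3, footnote a**, anchors the calendar: "All visits to be scheduled from the date of randomisation, not from the date of previous visit".

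Section 8.4 sets the safety definition: "any dose of study intervention greater than 280 mg administered within a 2-week period will be considered an overdose".

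**The concern.** Once the window has closed, and for any reason on the Section 6.2.3 list, the two sections point in opposite directions. One omits the dose. The other has it given at the earliest opportunity and asks that none be missed. Neither cross-refers to the other or claims precedence, and Section 6.5 is also at odds with its own preceding sentence. For a reason off the list, the only rescheduling text for a dose is that of Section 6.5.

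Two things are at stake. The first is uniform conduct: the same participant could be dosed at one site and skipped at another. That difference reaches the compliance percentage (SAP 3.6.1), the count of important deviations under the investigational product category (SAP 2.2), and the PK summary, which keeps Week 4 to 52 samples only if taken 21 to 35 days after the previous dose (SAP 4.2.11.1). The second is safety: the next visit does not move with a late dose, so lateness shortens the following interval. Neither document states a minimum interval between consecutive doses.

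**Working it through.** **Inputs.** Dose 210 mg every 28 days (Protocol 6.1.1 and 6.2.3). Treatment window ±5 days (Schedule of Activities; SAP 3.1.3 uses the same 28 and 5). Visits counted from randomisation (footnote a). Overdose: more than 280 mg within a 2-week period (8.4), read as a cumulative amount, which its wording supports.

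**Stated dose reproduced.** 110 mg/mL × 1.91 mL = 210.1 mg, which agrees with 210 mg. One dose is below 280 mg. Two doses are 2 × 210 = 420 mg, above it (420/280 = 1.5).

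**Gap formula.** Let a dose be given L days after its target day, and the next at offset e from its own target, with e from −5 to +5. Then

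gap = 28 + e − L.

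**If every dose is in its window or skipped.** The shortest gap is 28 − 5 − 5 = 18 days. The longest between consecutive given doses is 28 + 5 + 5 = 38 days. Two doses never share a 2-week period.

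**If a dose may be given after its window:**

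| Next dose | Gap under 14 days from | Gap of 14 days or less from |
|---|---|---|
| 5 days early (e = −5) | L = 10 | L = 9 |
| on target (e = 0) | L = 15 | L = 14 |
| 5 days late (e = +5) | L = 20 | L = 19 |

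The middle column treats a gap of exactly 14 days as outside the 2-week period. The right column treats it as inside. Section 8.4 does not say which applies. A dose 6 to 8 days late leaves at least 28 − 5 − 8 = 15 days and meets the definition on neither count.

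**Week 24 route (8.1.4).** If the last steroid dose falls on the Week 24 target day, the visit is at L = 14 or later. At L = 14, an in-window Week 28 dose follows 14 + e days later, that is 9 to 19 days. A steroid course ending later makes L larger. Steroid use is not itself on the Section 6.2.3 list.

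**Vaccine route (6.4.2).** The branch that allows rescheduling or skipping covers a vaccine v days after a dose with v at most 13. If that dose was on target, the next is no earlier than day v + 28, so L = v. At v = 13 the following dose comes 15 days later if on target and 28 − 5 − 13 = 10 days later if 5 days early.

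**PK consequence.** If the dose just before a PK visit is more than 7 days late, a sample on target is taken at most 28 − 8 = 20 days after it and drops out of the 21-to-35-day summary.

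**The case against.** The strongest reply has four parts.

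1. **Specific over general.** Section 6.2.3 governs named reasons and Section 6.5 is general, so the specific rule could be taken to prevail. The sentence before the disputed one in Section 6.5 also ties dosing to the windows. This is a fair reading, but no text adopts it. It also leaves reasons off the list, including the Week 24 move, to the wording of Section 6.5.
2. **Vaccination is already handled.** Section 6.4.2 keeps study visits in window, Section 6.2.3 includes planned vaccination in its skip rule, and sites are told to consult the study physician on intervals. A reader might infer that the rescheduling branch of Section 6.4.2 covers vaccination 14 or 20 days after a dose and so leads straight to an overdose. It does not: it stops short of 14 days. Nor is it an error that full vaccine spacing (14 + 28 = 42 days) exceeds the longest in-window gap of 38 days. The spacing is a recommendation that anticipates skipped or moved doses. What stands is that the branch allows either course and so does not settle which rule applies.
3. **The boundary.** Several simple cases give exactly 14 days. Section 4.3 mentions a studied 280 mg every-2-weeks regimen, which suggests that a 14-day gap is not meant to count. That is an inference, because the protocol does not explain its threshold. It moves the limits by one day and removes none of them.
4. **Consequences.** A reader might infer that a participant dosed under Section 6.5 automatically becomes an adverse event, or that the efficacy result is at risk. Neither is supported. An overdose without symptoms is recorded only on the Overdose module, although the sponsor must still be told within 24 hours. Adherence to study product is handled by treatment policy in the primary estimand (Protocol 9.4.1.1, SAP 4.1.3.1).

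**Conclusion.** The contradiction is real and should be resolved. For the reasons listed in Section 6.2.3, the two sections give incompatible instructions once the window has closed. For other reasons, only the open-ended wording of Section 6.5 applies, against its own preceding sentence.

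Two consecutive scheduled doses can meet the overdose definition only if the first is given well after its window: at least 10 days after target when the next is 5 days early, 15 when it is on target, 20 when it is 5 days late, or one day less in each case if a 14-day gap counts. This assumes that the definition is cumulative and that the next dose is not itself deferred.

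It would go too far to say that every late dose is an overdose, that Section 6.2.3 skips every dose that misses its window whatever the reason, or that vaccination alone brings the event about. The documents do not allow the frequency to be estimated. No effect on the primary efficacy conclusion is claimed.

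**What to change.** Reconcile Sections 6.2.3, 6.4.2, 6.5 and the V10 sentence of Section 8.1.4 into one rule for a dose that cannot be given in its window, whatever the reason. State whether product moves with a rescheduled visit. Check the chosen rule against footnote a and the Section 8.4 definition, and say whether doses exactly 14 days apart fall in the same 2-week period. Cross-refer Section 6.5 to Section 6.2.3. The choice of rule is a clinical decision for the sponsor, and none is proposed here.

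The cost is a few sentences in the next amendment or a clarification memo to sites, with no new procedures or data.
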